## 1. PROTOCOL SUMMARY

### 1.1. Synopsis

**Name of Sponsor/Company:** ModernaTX, Inc.

**Name of Investigational Products:** mRNA-1011.1, mRNA-1011.2, and mRNA-1012.1, and mRNA-1010 products (mRNA-1010, mRNA-1010.2 and mRNA-1010.3)

**Protocol Number:** mRNA-1011-P101

**Protocol Title:** A Phase 1/2, randomized, open-label study to evaluate the safety, reactogenicity, and immunogenicity of mRNA-1011.1, mRNA-1011.2, and mRNA-1012.1 candidate seasonal influenza vaccines in healthy adults 50 to 75 years of age

**Brief Title:** A Phase 1/2 study to evaluate the safety, reactogenicity, and immunogenicity of mRNA-1011.1, mRNA-1011.2, and mRNA-1012.1 influenza vaccines in healthy adults 50 to 75 years of age

**Regulatory Agency Identifier Number:** Not yet available

### Background and Rationale:

Currently licensed seasonal influenza virus vaccines have suboptimal efficacy, rarely exceed 50% overall effectiveness, and are poorly effective during years when the circulating viruses do not match the strains selected for the vaccine antigens ([CDC 2020](#)). Influenza vaccines based on mRNA technology could provide several benefits compared to current vaccines, including the ability to respond to strain changes more quickly, avoidance of mutations that may be acquired during vaccine production in eggs or cell culture, potential for stronger immune responses, as well as improved protection in older adults ([Rockman et al 2020](#)).

Current quadrivalent seasonal influenza vaccines are manufactured to prevent influenza illness caused by 4 influenza strains that include 2 influenza A strains (A/H1N1 and A/H3N2) and 2 influenza B strains (B/Yamagata and B/Victoria). However, influenza A/H3N2 remains the major driver of influenza-related hospitalizations and deaths, particularly in older adults. Lower vaccine effectiveness against the influenza A/H3N2 viruses may be in part caused by vaccine mismatches that can occur due to co-circulation of multiple different A/H3N2 clades, whereas only one of those clades is generally covered by the vaccine. The inclusion of additional strains could allow for expanded coverage against multiple co-circulating A/H3N2 strains of distinct antigenic clades in influenza vaccination programs; and furthermore, enable public health authorities to recommend a higher number of strains for inclusion into the vaccine.

The Sponsor is conducting this Phase 1/2 study to evaluate safety and immunogenicity of 3 next-generation seasonal influenza mRNA vaccines with coverage for more than one A/H3N2 strain (mRNA-1011.1, mRNA-1011.2, and mRNA-1012.1) compared to the quadrivalent mRNA-1010 vaccine with coverage for 1 A/H3N2 strain. mRNA-1011.1 contains 5 mRNAs encoding hemagglutinin antigens (HAs) for A/H1N1, B/Victoria, B/Yamagata, and two A/H3N2 strains, while mRNA-1011.2 contains 4 mRNAs encoding HAs similar to mRNA-1011.1 (including coverage for two A/H3N2 strains) but with B/Yamagata excluded. The rationale for excluding B/Yamagata is due to the lack of circulation of B/Yamagata-lineage viruses in recent years and thus, allowing for a higher proportion of other strains to be represented in the vaccine

within the same total mRNA dose. mRNA-1012.1 contains 5 mRNAs encoding HAs similar to 1011.2 but with 1 additional HA from the A/H3N2 lineages (coverage for three A/H3N2 strains).

The comparator mRNA-1010 vaccine is the Sponsor's first-generation quadrivalent vaccine containing HAs from A/H1N1, B/Yamagata, B/Victoria, and 1 of three A/H3N2 lineages that matches those in the next-generation vaccines (mRNA-1010, mRNA-1010.2, and mRNA-1010.3). The mRNA-1010 vaccine is currently under investigation in an ongoing Phase 3 immunogenicity study in adults  $\geq 18$  years of age ([NCT05415462](#)) and Phase 3 efficacy study in adults  $\geq 50$  years of age ([NCT05566639](#)).

The objective of the study (mRNA-1011-P101) is to establish preliminary safety and immunogenicity data to support selection of a lead candidate for initiation of pivotal studies. The mRNA-1011.1, mRNA-1011.2, mRNA-1012.1, and mRNA-1010 (mRNA-1010, mRNA-1010.2, and mRNA-1010.3) development candidates are administered as a single dose and are aimed to elicit protection from all seasonal influenza viruses covered by the candidate vaccines.

The study design has safety and reactogenicity evaluation as the primary objective, with a secondary objective of evaluating immunogenicity for each HA component using the HAI assay, because HAI titers have been established as a correlate of protection against influenza illness. The rationale for this approach is based on the established precedent of using HA-based immunologic correlates for clinical assessment and licensure of influenza vaccines ([DHHS 2007a](#); [EMA Guidance 2016](#); [Dunning et al 2016](#)).

## Objectives and Endpoints

Objectives	Endpoints
Primary	

 
To evaluate the safety and reactogenicity of mRNA-1011.1, mRNA-1011.2, mRNA-1012.1, and mRNA-1010 controls (mRNA-1010, mRNA-1010.2 and mRNA-1010.3)
 
	
 
Solicited local and systemic ARs through 7 days after injection
 
Unsolicited AEs through 28 days after injection
 
MAAEs from Day 1 to Day 181/EoS
 
AESIs from Day 1 to Day 181/EoS
 
SAEs from Day 1 to Day 181/EoS
 
AEs leading to discontinuation from Day 1 to Day 181/EoS
 

Secondary	

 
To evaluate the humoral immunogenicity of mRNA-1011.1, mRNA-1011.2, mRNA-1012.1 in comparison with mRNA-1010 controls (mRNA-1010, mRNA-1010.2 and mRNA-1010.3) against vaccine-matched
 
	
 
GMT and GMFR, comparing Day 29 with Day 1 (baseline), and percentage of participants with seroconversion, defined as a postbaseline titer <math>\geq 1:40</math> if baseline is <math>< 1:10</math> or a 4-fold or greater rise if baseline is <math>\geq 1:10</math> in
 

Objectives	Endpoints
influenza A and B strains at Day 29	anti-HA antibodies measured by HAI assay

Abbreviations: AE = adverse event; AESI = adverse event of special interest; EoS = end of study; GMFR = geometric mean fold rise; GMT = geometric mean titer; HA = hemagglutinin; HAI = hemagglutination inhibition; MAAE = medically attended adverse event; mRNA = messenger ribonucleic acid; SAE = serious adverse event.

## Overall Study Design

This prospective, open-label Phase 1/2 study will enroll approximately 700 healthy adults  $\geq 50$  to  $\leq 75$  years of age. Participants will be stratified by prior season influenza vaccination status; those who received a licensed or investigational influenza vaccine within 180 days prior to enrollment will be excluded. Different dose levels will be assessed in parallel across 7 treatment arms. Each participant will receive a single injection administered intramuscularly in the deltoid muscle and will be followed for 6 months post vaccination.

## Brief Summary

The purpose of this study is to measure the safety and the immune response to 3 next-generation influenza vaccine candidates (mRNA-1011.1, mRNA-1011.2, and mRNA-1012.1) compared with influenza vaccine candidate mRNA-1010 controls in healthy adult participants. The study duration will be up to 7 months including screening. The treatment will be administered as a single dose on Day 1.

Key study details include:

- Screening Visit (up to 28 days before the Day 1 visit).
- Randomization Visit at Day 1 (Baseline).
- Subsequent study visits will occur on Day 8, Day 29 (Month 1), and Day 181 (Month 6)/EoS.
- Five safety telephone call visits at Days 15, 57, 91, 121, and 151 will be conducted.
- Unscheduled visits for protocol-defined influenza-like illness (ILI) symptoms. Symptom assessment and collection of NP sample should be performed  $\leq 7$  days from onset of ILI symptoms.
- All participants will be asked to complete an eDiary for solicited ARs from Day 1 to Day 7.

**Number of Participants:** Approximately 700 participants will be enrolled into 7 treatment arms.

[figure not shown]
**Note:** Enrolled means participants agree to participate in a clinical study following completion of the informed consent process and screening. Potential participants who are screened for the purpose of determining eligibility for the study, but do not participate in the study, are not considered enrolled unless otherwise specified by the protocol.

## Study Arms and Duration:

- The study comprises 7 treatment arms of different dose levels of drug products with 6-month follow-up post vaccination.
- The total duration (including screening) for each participant is up to 7 months.

## 1.2. Schema

Figure 1: Study Schema

Abbreviation: C = Clinic; D = Day; mRNA = Messenger ribonucleic acid; N = Number of participants; SC = Safety Call; V = Visit

### 1.3. Schedule of Events

**Table 1: Schedule of Events**

Visit Number	SCRN	1	2	3	4	5, 6, 7, 8	9	USV
Type of Visit	C	C	C	SC	C	SC	C	C
Month Timepoint					M1	M2, M3, M4, M5	M6	Up to M6
Visit Day	Screening a	D1 (Baseline) a	D8	D15	D29	D57, D91, D121, D151	D181/ EoS	N/A
Window Allowance (Days)	-28	-	-1/+3	±3	-7/+3	±5	±14	N/A
Informed consent form, demographics, concomitant medications, medical history	X							
Inclusion/exclusion criteria	X	X						
Blood collection for safety laboratory samples b	X		X					
Physical examination c	X	X	X		X		X	X
Injection site and corresponding draining lymph nodes assessment d		X						
Vital sign measurements e	X	X						
Pregnancy testing f	X	X						
Randomization		X						
Study vaccination (including 60-minute, postdose observation period)		X g						
Blood collection for humoral immunogenicity h		X			X		X	
Blood collection for cellular immunogenicity h		X			X			
Optional blood collection for genomics i		X						
Optional blood collection for transcriptomics i		X	X		X			

Visit Number	SCRN	1	2	3	4	5, 6, 7, 8	9	USV
Type of Visit	C	C	C	SC	C	SC	C	C
Month Timepoint					M1	M2, M3, M4, M5	M6	Up to M6
Visit Day	Screening a	D1 (Baseline) a	D8	D15	D29	D57, D91, D121, D151	D181/ EoS	N/A
Window Allowance (Days)	-28	-	-1/+3	±3	-7/+3	±5	±14	N/A
Nasopharyngeal swab for virus detection j		X						X
eDiary activation for recording solicited ARs (7 days) k		X						
Review of solicited AR eDiary			X					
Follow-up safety call l				X		X		
Recording of unsolicited AEs through Day 29 and concomitant medications		X	X	X	X			X
Recording of SAEs, AESIs, MAAEs, AEs leading to discontinuation, and concomitant medications relevant to or for their treatment		X	X	X	X	X	X	X
Recording of nonstudy vaccinations	X	X	X	X	X	X	X	
Study completion							X	

Abbreviations: AE = adverse event; AESI = adverse event of special interest; ALT = alanine aminotransferase; AR = adverse reaction; AST = aspartate aminotransferase; C = clinic visit; D = day; eDiary = electronic diary; EoS = end of study; FSH = follicle-stimulating hormone; HCP = health care practitioner; ILI = influenza-like illness; IM = intramuscular; M = month; MAAE = medically attended adverse event; N/A = not applicable; NP = nasopharyngeal; SAE = serious adverse event; SC = safety (telephone) call; SCRN = Screening; USV = unscheduled visit.

- a Screening and Day 1 cannot be performed on the same day. Additionally, the Screening Visit may be performed over multiple visits if within the 28-day Screening window.
- b Safety laboratory tests include total white blood cell count, hemoglobin, platelets, ALT, AST, creatinine, alkaline phosphatase, and total bilirubin.
- c A full physical examination, including height and weight, will be performed at Screening; symptom-directed physical examinations will be performed at other clinic visits. Interim physical examinations will be performed at the discretion of the Investigator. Any clinically significant finding identified by an HCP during clinic visits should be reported as a MAAE.

- d Prior to injection on the day of vaccination (Day 1), the injection site and associated draining lymph nodes (ipsilateral axillary lymph nodes) should be examined, and any abnormalities should be documented.
- e Systolic and diastolic blood pressure, pulse rate, respiratory rate, and body temperature will be recorded as vital signs. The preferred route of temperature assessment is oral. Vital signs will only be collected at Screening and on the day of vaccination (Day 1), once before and at least 60 minutes after vaccination. Vital signs will be collected at other clinical visits only in conjunction with a symptom-directed physical examination.
- f A point-of-care urine pregnancy test will be performed at the Screening Visit and before the IM injection on Day 1. At the discretion of the Investigator, a pregnancy test either via blood or point-of-care urine can be performed at any time. The FSH level may be measured at the Screening Visit, if necessary and at the discretion of the Investigator, to confirm menopausal status.
- g All participants will be randomized to receive a single IM injection in the deltoid muscle.
- h Samples for humoral immunogenicity and cellular immunogenicity must be collected prior to receipt of vaccination on Day 1. Cellular immunogenicity will be sampled and assessed in a subset of approximately 15 to 20 participants per arm.
- i Transcriptomic and genomic samples will be part of the optional biomarker assessment once consented by participants. Blood draws on Day 1 must occur prior to participants being vaccinated.
- j An NP swab specimen for viral respiratory pathogens will be collected prior to the study intervention administration on Day 1. An NP swab should be collected through study completion for protocol-defined ILI  $\leq$  7 days of symptom onset.
- k The eDiary entries will be recorded by the participant starting approximately 60 minutes after vaccination while at the clinic with instruction provided by study staff. Study participants will continue to record in the eDiary each day after vaccination, on the day of vaccination and for subsequent 6 days following vaccination.
- l Trained study personnel will call all participants to collect information related to any SAEs, MAAEs, AESIs, or AEs leading to study discontinuation, with information on concomitant medications associated with those events, and any nonstudy vaccinations.

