#### **6.7.2. Concomitant Medications and Vaccinations**

The following information regarding concomitant medication and vaccinations will be recorded in the eCRF:

- All nonstudy vaccinations administered within the period starting 28 days before the study intervention and through Day 181 (Month 6)/EoS.
- Any authorized or investigational COVID-19 vaccine at any time before the study intervention and through Day 181 (Month 6)/EoS.
- All concomitant medications taken through 28 days after the study intervention. Antipyretics and analgesics taken prophylactically (ie, taken in the absence of any symptoms in anticipation of an injection reaction) will be recorded as such.
- Systemic steroids ( $\geq 10$  mg/day of prednisone or equivalent), immunosuppressants, immunoglobulins, or long-acting biological therapies that affect immune responses (eg, infliximab), or blood products administered at any time during the study period after the study intervention.
- Any concomitant medications relevant to or for the treatment of a SAE, AESI, or MAAE from Day 1 through Day 181 (Month 6)/EoS.
- The participant will be asked in the eDiary if they have taken any antipyretic or analgesic medication to treat or prevent fever or pain within 7 days after the study intervention, including the day of injection. Reported antipyretic or analgesic medications should be recorded in the source document by the study site staff during the study visits after vaccination or via other participant interactions (eg, telephone calls).

Concomitant medications (including vaccinations) will be coded using the WHO Drug Global Dictionary.

It is the Investigator's responsibility to ensure that details regarding the concomitant medications are adequately recorded in the eCRF.

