## 8. STUDY ASSESSMENTS AND PROCEDURES

Before performing any study procedures, all potential participants will sign an informed consent form ([Section 11.1.6](#)). Participants will undergo study procedures at the timepoints specified in the SoE ([Table 1](#)).

A participant can also be seen for an unscheduled visit at any time during the study. Reasons for an unscheduled visit may include, but are not limited to, reactogenicity issues, symptoms of potential ILI, and new or ongoing AEs. The site also has discretion to make reminder telephone calls or send text messages to inform the participant about visits, review eDiary requirements, or follow-up on ongoing or outstanding issues.

General considerations for study assessments and procedures include the following:

- Protocol waivers or exemptions are not allowed. The study procedures and their timing must be followed as presented in the SoE ([Table 1](#)). Adherence to the study design requirements is essential and required for study conduct.
- Immediate safety concerns should be discussed with the Sponsor immediately upon occurrence or awareness to determine if the participant should continue participation in the study.
- All screening evaluations must be completed and reviewed to confirm that potential participants meet all eligibility criteria. The Investigator will maintain a screening log to record details of all participants screened and to confirm eligibility or record reasons for screening failure, as applicable.
- The Screening Visit and Day 1 Visit will not be performed on the same day. The Screening Visit may be performed over multiple visits if within the 28-day screening window.

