### 8.2. Safety Assessments and Procedures

Safety assessments will include monitoring and recording of the following for each participant, according to the SoE ([Table 1](#)):

- Solicited local and systemic ARs ([Section 8.4.4](#)) that occur during the 7 days following the study intervention (ie, the day of study vaccination [Day 1] and 6 subsequent days). Solicited ARs will be recorded daily using eDiaries.
- Unsolicited AEs observed or reported within 28 days following the study intervention, with the day of study vaccination as Day 1 ([Section 8.4.2](#)).

- AEs leading to discontinuation from study participation from Day 1 through Day 181 (Month 6)/EoS or withdrawal from the study.
- MAAEs from Day 1 through Day 181 (Month 6)/EoS or withdrawal from the study ([Section 8.4.5](#)).
- AESIs from Day 1 through Day 181 (Month 6)/EoS or withdrawal from the study ([Section 8.4.6](#)).
- SAEs from Day 1 through Day 181 (Month 6)/EoS or withdrawal from the study ([Section 8.4.3](#)).
- Results of abnormal safety laboratory tests ([Section 8.2.12](#)).
- Abnormal vital sign measurements ([Section 8.2.1](#)).
- Abnormal physical examination findings ([Section 8.2.1](#)).
- Details of all pregnancies in female participants will be collected from Day 1 through Day 181 (Month 6)/EoS ([Section 8.2.2](#)).

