### **8.2.4. Safety Telephone Calls**

A safety telephone call will be made to the participant by trained study site staff using a script to facilitate the collection of relevant safety information. Safety telephone calls will follow a schedule for each participant, as shown in the SoE ([Table 1](#)). The participant will be interviewed according to the script about occurrence of AEs, MAAEs, SAEs, AESIs, AEs leading to withdrawal from study participation, concomitant medications associated with those events, and any nonstudy vaccinations. All safety information collected from the telephone call must be documented in source documents as described by the participant and not documented on the script used for the safety telephone contact. An unscheduled follow-up safety call may be triggered if an eDiary record results in identification of a relevant safety event.

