### **8.2.7. Recording and Follow-up of an AE and/or SAE**

The Investigator is responsible for ensuring that all AEs and SAEs are recorded in the eCRF and reported to the Sponsor.

Solicited ARs will be collected from Day 1 through 7 days after the study intervention (ie, the day of study vaccination and 6 subsequent days). Other (unsolicited) AEs will be collected from Day 1 through 28 days after the study intervention (ie, the day of study vaccination and 27 subsequent days).

MAAEs, SAEs, and AESIs will be collected from participants as specified in the SoE ([Table 1](#)) from Day 1 until the end of their participation in the study. Any AEs occurring before receipt of the study intervention will be analyzed separately from TEAEs.

At every study site visit or telephone contact, participants will be asked a standard set of questions to elicit any medically related changes in their well-being (including surveillance for respiratory viral infection symptoms) according to a provided script. Participants will also be asked if they have been hospitalized, had any accidents, used any new medications, changed concomitant medication regimens (both prescription and over-the-counter medications) or had any nonstudy vaccinations.

In addition to participant observations, physical examination findings and other documents relevant to participant safety classified as an AE will be documented in EDC.

After the initial AE/SAE report, the Investigator is required to proactively follow each participant at subsequent visits/contacts. All AEs and SAEs will be treated as medically appropriate and followed until resolution, stabilization, the event is otherwise explained, or the participant is LTFU (as defined in [Section 7.4](#)).

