### **8.2.8. Reporting Adverse Events**

The Investigator is responsible for reporting all AEs that are observed or reported during the study, regardless of their relationship to the study intervention or their clinical significance. If there is any doubt as to whether a clinical observation is an AE, the event should be reported.

All unsolicited AEs reported or observed during the study will be recorded in EDC. Information to be collected includes, type of event, time of onset, Investigator specified assessment of severity (impact on activities of daily living) and relationship to study intervention, time of resolution of the event, seriousness of event, as well as any required treatment or evaluations, and outcome. The unsolicited AEs resulting from concurrent illnesses, reactions to concurrent illnesses, reactions to concurrent medications or progression of disease states must also be reported. All AEs will be followed until they are resolved, stable or judged by the Investigator to be not clinically significant. The MedDRA will be used to code all unsolicited AEs.

Refer to [Section 8.2.10](#) for reporting of medical occurrences that begin before study intervention administration but after obtaining informed consent.

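### Are ordinary adverse events and medications lost at the end of the 28-day window when the Day 29 visit is held early?

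*Protocol*

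**What the plan says.** Unsolicited adverse events over 28 days are a primary endpoint (Protocol Table 2, SAP 3.1). Protocol 8.2.7 and SAP 6.1 both define the window as the vaccination day plus 27 days, that is, Days 1 to 28. For medications, Protocol 6.7.2 asks for "All concomitant medications taken through 28 days after the study intervention", and SAP 6.2.4 tabulates them over 28 days.

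Two places describe collection narrowly:

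- **Table 1.** The row "Recording of unsolicited AEs through Day 29 and concomitant medications" is marked at Days 1, 8, 15 and 29 and at unscheduled visits. It is blank for the Day 57, 91, 121 and 151 calls and for Day 181. The Day 29 visit has a window of -7/+3 days.
- **Footnote l, on the safety calls.** "Trained study personnel will call all participants to collect information related to any SAEs, MAAEs, AESIs, or AEs leading to study discontinuation", plus the medications for those events and nonstudy vaccinations.

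Three places describe it more fully:

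- **Section 8.2.4.** At each safety call the participant is "interviewed according to the script about occurrence of AEs, MAAEs, SAEs, AESIs" and events leading to withdrawal.
- **Section 8.2.7.** "At every study site visit or telephone contact, participants will be asked a standard set of questions to elicit any medically related changes". The same set of questions covers new or changed medications.
- **Section 8.2.8.** "All unsolicited AEs reported or observed during the study will be recorded in EDC".

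**The concern.** Read on its own, the schedule stops asking about ordinary events at the Day 29 visit, wherever in its window that visit falls. A participant seen on Day 22 has six days of the window still to run. At the next scheduled contact, the Day 57 call, Table 1 shows no tick in this row and footnote l names only the special categories. Section 8 adds weight to that reading: "The study procedures and their timing must be followed as presented in the SoE". The catch-up rule in Section 6.4 does not help, because it concerns missed visits and a Day 22 visit is within its window.

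The description of the window also varies. The Table 1 row label runs to Day 29, Section 8.2.7 stops at Day 28, and Section 8.2 speaks of "Unsolicited AEs observed or reported within 28 days following the study intervention". Taken literally, that last phrase could shut out a Day 25 event first mentioned at the Day 57 call.

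At stake would be under-counting of events that are non-serious, not medically attended, not of special interest, and not a cause of discontinuation or an unscheduled visit. Routine medications in the same days would be affected too. Sites might also differ in what they ask.

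**Working it through.** **The plan's own figure.** Protocol Table 8 gives 86.7% for seeing at least one event with n = 100 and a true rate of 2%. Check: 1 - (1 - 0.02)^100 = 86.7%. It reproduces. It takes the full window as observed.

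**Days left after the visit.** Inputs from Table 1 and Section 8.2.7: the visit falls between Day 29 - 7 = 22 and Day 29 + 3 = 32, and the window ends on Day 28. Days left = max(0, 28 - visit day).

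| Visit day | 22 | 23 | 24 | 25 | 26 | 27 | 28 to 32 |
|---|---|---|---|---|---|---|---|
| Days left | 6 | 5 | 4 | 3 | 2 | 1 | 0 |

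The next call is on Day 57 ± 5, that is, Days 52 to 62. Onset on Days 23 to 28 would be recalled after 52 - 28 = 24 to 62 - 23 = 39 days.

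**Size if nobody asked at that call.** The documents give neither a visit-day distribution nor an adverse event rate, so everything here is assumed.

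- Ceiling, with every participant seen on Day 22: 6/28 = 21.4% of the window. With a constant hazard and a true 28-day incidence of 10%, the observed incidence would be 1 - 0.9^(22/28) = 7.9%. On the Table 8 scale, 86.7% would become 1 - 0.98^(100 × 22/28) = 79.6%.
- More moderate cases, with a share f seen evenly over Days 22 to 27: the mean number of days left is (6+5+4+3+2+1)/6 = 3.5, so the exposed part is f × 3.5/28. For f = 10% this is 1.25%, and for f = 30% it is 3.75%. If all 11 permitted days were equally likely, f = 6/11 and the exposed part is 6.8%.

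So the loss would not be negligible in the extreme case. What matters is whether the call asks.

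**Does the call ask?**

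1. Section 8.2.4 lists adverse events separately from the medically attended, serious and special-interest categories, so ordinary events are in the call script.
2. Section 8.2.7 applies to every telephone contact without exception, and covers medications as well as health changes.
3. Footnote l does not say that calls are limited to the categories it names, and a blank cell prohibits nothing. Section 8 makes the schedule binding but does not make it exhaustive. A site can follow Table 1, footnote l, 8.2.4 and 8.2.7 together.
4. Section 8.2.8 requires a reported event to be entered whenever in the study it is reported. That answers the literal reading of Section 8.2.
5. SAP 6.4.2 counts events by occurrence, and SAP Table 5 classifies medications by start and stop dates. A Day 25 event or medication recorded at the Day 57 call enters the 28-day tables.

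**The case for a change.** The strongest case for a change is that this is a primary endpoint, that sites tend to work from the schedule, and that an edit to a footnote costs almost nothing. Several parts of that case stand. Footnote l is narrower than its own table: it covers the Day 15 call, where Table 1 does mark the row, yet it does not mention ordinary events. The general medication question at calls rests on Section 8.2.7 alone, since Section 8.2.4 asks only for medications linked to events. Recall of 24 to 39 days is long for a mild event. The interim analysis follows completion of Day 29 and could precede some Day 57 calls, so a late event in a participant seen early might be missing from it.

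None of this leads to a different plan. An amended footnote would restate what 8.2.4 and 8.2.7 already require, on the same call and with the same recall. It would do nothing for an interim analysis run before that call. The three descriptions of the window have little effect, because the row label includes Day 28 and the analysis window in the SAP is unambiguous. That sites would differ is conjecture, since the protocol provides a script for these questions.

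A small loss relative to the confidence interval at n = 100 is not a good defence, because under-capture is systematic and sampling error is not. The defence is that the plan already provides for capture.

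**Conclusion.** The observation is accurate but calls for no change. For participants seen on Days 22 to 27, the last 6 to 1 days of the window are covered by Sections 8.2.4 and 8.2.7 and not by the Table 1 row. The row and footnote l are incomplete summaries of the call content, which is a clerical slip.

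The expected effect on the results is none if sites follow the whole protocol. This assumes that the call script, which is not among the documents, contains the questions those two sections describe. If it did not, the exposed part of the window could not exceed 21.4%. It would be 1.25% to 6.8% under the assumed visit patterns above, before any allowance for spontaneous reports, unscheduled visits, or influenza-like illness recorded as an adverse event through Day 28 (Section 8.4.1). Serious, medically attended, special-interest and discontinuation events are collected at every contact in any case. All seven arms share one schedule, no arm difference is shown, and the analysis is descriptive with no formal hypothesis.
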